ActiGraph wGT3X-BT Accelerometer

PROMIS depression v1.08b

PROMIS anxiety v1.08a

Pain Catastrophizing Scale (PCS)

Tampa Kinesiophobia Scale (TSK)

Measure of Current Status (MOCS)

Cognitive and Affective Mindfulness Scale (CAMS)

Modified Global Impression of Change (MGIC) – only at post-test

Credibility/Expectancy Questionnaire (CEQ) (post-tests or as soon as possible after post-tests)

Client Satisfaction Questionnaire (CSQ-3) (post-tests or as soon as possible after post-tests)

Fitbit Use (GetActive Only)- only at 6-month follow-up

Table 1. Study Procedures		
Time	Task	Details
6-7 Weeks Before Intervention	Recruitment and Screening	RA receives referrals, screens via telephone, records availability for eligible participants
3 Weeks Before Intervention	Scheduling	RA selects baseline time based on participant availability. RA calls participants to confirm time.
~1 Week Before Intervention	Consent and Baseline Assessment	Review and sign consent. Participants complete: self-report measures, 6-minute walk test, Participants also receive ActiGraph devices and instructions.
10-Week Intervention	Group Sessions 1-10	Participants complete 10 weeks of group sessions of either GetActive-Fitbit or Healthy Living for Pain .  Sessions will be audio recorded, to ensure accuracy of delivery and assess fidelity.
1 Week Post Intervention	Post-Intervention Assessments	Participants repeat procedures from the baseline assessment. Participants return ActiGraph devices after the post-test assessment in person.
2 Weeks Before 6-Month Assessments	ActiGraphs Mailed Out	RA mails ActiGraphs to participants to be worn in week prior to 6-Month Follow up
6 Months Post Intervention	6-Month Follow-Up Assessments	Participants repeat procedures from the baseline and post-test assessments. Participants return ActiGraph devices after the 6-month follow-up assessment in person.

Participants will be paid \$945 for completing the study in its totality. If participants do not complete the study, we will pay based on the following study visits and tasks completed:

- For the baseline assessment, participants will receive \$60 for the completion of study tasks and up to \$100 additional dollars for ActiGraph wear (\$10 dollar per day, plus an additional \$30 for 7 days with complete valid wear).

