## **9. Statistical Analysis**

We plan to enroll N=120 participants across sites, with 40 participants recruited per site. We believe that this sample size is appropriate for a feasibility trial, including similar proposals previously funded NCCIH (e.g., 1U01AT010462). The proposed sample provides good power to achieve our multisite fidelity and feasibility benchmarks. Specifically, if 90 participants are enrolled, the study will have an 80% probability of meeting all seven Aim 2 feasibility benchmarks if the expected proportion of participants enrolling, completing at least 7 of 10 sessions, rating the program as credible and satisfactory, and completing post-treatment follow-up is at least 89% and if the expected proportion of protocol checklists deemed accurate is at least 95%. Moreover, the planned sample size will provide adequate precision for estimating fidelity and feasibility benchmarks.

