### **Statistical analyses:**

First, we will report:

- percent eligible sedentary chronic pain patients who enroll after being determined eligible during screening (benchmark  $\geq 80\%$  AND 34/90 racial and ethnic minorities).

- Total duration of recruitment in months overall and at each site.
- Percent of patients who attend  $\geq 7/10$  sessions for each program (benchmark is 80%).
- Percent patients with credibility scores higher than the scale's mid point (Credibility and Expectancy scale; benchmark is 80%)
- Percent patients with satisfaction scores higher than the scale's mid point (Client Satisfaction scale; benchmark is 80%)
- Percent patients who complete post-treatment (benchmark is 80%) and 6 months follow up (benchmark is 70%) including self-report, performance based and Actigraph valid data.
- Percent accuracy of standardized protocol checklists for all assessments (benchmark is 90% accuracy).
- We will also report additional information necessary to complete the CONSORT diagram.

Next, we will use Fisher's exact tests to make comparisons of number of people meeting each benchmark across sites and between the intervention arms, while also plotting performance metrics across sites to account and assess for trends in differences due to the low statistical power.

Estimates of variance components required for design of a future efficacy trial will be obtained from preliminary analysis of outcome report, performance based, and objective/ambulatory measurements in mixed model repeated-measures analyses.

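### Arms are compared on credibility, satisfaction and attendance only by Fisher's exact test on cut-offs; score differences with confidence intervals should be added

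*Combined protocol and SAP*

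**What the plan says.** Section 9 (Statistical analyses) defines the credibility result as "Percent patients with credibility scores higher than the scale's mid point (Credibility and Expectancy scale; benchmark is 80"%). Satisfaction is treated the same way, and attendance is the share attending at least 7 of 10 sessions. The arms are then compared by Fisher's "exact tests to make comparisons of number of people meeting each benchmark across sites and between the intervention arms". The same sentence acknowledges low power and adds plots of performance across sites; it offers none between arms.

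The underlying measurements are available. Section 6 lists the "Credibility/Expectancy Questionnaire (CEQ) (post-tests or as soon as possible after post-tests") and the CSQ-3 at the same time point, in both arms. Section 9 plans no mean, standard deviation, interval or score-based arm comparison for either. Its mixed models cover the self-report, performance-based and ambulatory outcome measures, and serve to obtain variance components.

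On size, Section 9 states "We plan to enroll N=120 participants across sites, with 40 participants recruited per site". Its probability statement rests on a smaller number: "if 90 participants are enrolled, the study will have an 80% probability of meeting all seven Aim 2 feasibility benchmarks". That statement assumes, among other things, that the proportion "rating the program as credible and satisfactory, and completing post-treatment follow-up is at least 89"%. No significance level, allocation ratio or credibility gap of concern is given.

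**The concern.** Where most participants in both arms are expected to exceed the cut-off, a yes/no split carries little information about how far apart the arms are. A clear shift in scores may move only a few people across the midpoint, and Fisher's test is conservative at these sample sizes.

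The comparison matters because the trial prepares for an efficacy trial of GetActive-Fitbit against HEP. If HEP is the less credible program, a later difference in outcome is harder to separate from expectancy. The sponsor already treats such contrasts as informative: Section 1 cites better attendance and credibility for GetActive-Fitbit than for GetActive in the single-site pilot when explaining which program goes forward.

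A smaller point is that comparing arms on each benchmark, taken literally, includes enrolment among eligible patients. Enrolment precedes randomization (Section 6), so it has no arm.

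**Working it through.** **The plan's own figure.** Section 9 gives an 80% probability of meeting all benchmarks with 90 enrolled. I used exact binomial tails multiplied as if independent, with five benchmarks at a true 89% and checklists at a true 95% ("expected proportion of protocol checklists deemed accurate is at least 95"%).

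- Pooled over arms: P(X ≥ 72 | 90, 0.89) = 0.996 and P(X ≥ 81 | 90, 0.95) = 0.985. The product 0.996⁵ × 0.985 is 0.967. The 6-month target of 70% adds a factor of about 1 if its true rate is also 89%.
- Per arm of 45: P(X ≥ 36 | 45, 0.89) = 0.9777. With all five benchmarks required in each arm and checklists pooled, 0.9777¹⁰ × 0.985 = 0.79. With enrolment also pooled, 0.9777⁸ × 0.996 × 0.985 = 0.82.
- The per-arm match is not unique. The pooled product also falls to 0.79 if the target of 34 minority participants in 90 is included at an assumed true share of 42%.

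The stated 80% is therefore reproducible, but it does not settle whether credibility is judged by arm or pooled.

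**Power of the arm comparison.**

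- From the plan: 120 enrolled, or 60 per arm; 90 enrolled, or 45 per arm; 89% above midpoint, given here to GetActive-Fitbit. At the 80% post-treatment completion benchmark, 60 × 0.80 = 48 per arm would be scored.
- Assumed: two-sided alpha 0.05, 1:1 allocation, HEP rates from 80% down to 65%, and normal underlying scores with equal spread.
- Score gap in SD units: d = Φ⁻¹(0.89) − Φ⁻¹(p for HEP). For 75%, d = 1.2265 − 0.6745 = 0.552.
- Fisher power: sum the binomial probabilities of all tables with p ≤ 0.05.
- Mean-score power: noncentral t with 2n − 2 degrees of freedom and noncentrality d√(n/2). For 75% and n = 60 this is 0.552 × √30 = 3.02, giving power 0.85.

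| HEP above midpoint | Gap (points) | d | Fisher, n = 45 / 48 / 60 | Mean scores, n = 45 / 48 / 60 |
|---|---|---|---|---|
| 80% | 9 | 0.38 | 0.14 / 0.15 / 0.20 | 0.44 / 0.46 / 0.55 |
| 75% | 14 | 0.55 | 0.31 / 0.33 / 0.43 | 0.74 / 0.76 / 0.85 |
| 70% | 19 | 0.70 | 0.52 / 0.55 / 0.67 | 0.91 / 0.93 / 0.97 |
| 65% | 24 | 0.84 | 0.71 / 0.75 / 0.85 | 0.98 or more |

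Against 89%, Fisher power reaches one half at a gap of about 16 points with 60 per arm, 18 with 48 and 19 with 45. It reaches 0.80 at about 22 to 27 points.

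**Sensitivity to normality.** A simulation at 89% against 75% used a bounded, rounded score (assumed 1 to 9 scale, SD 1.6). Power was 0.73 to 0.85 for the t-test, 0.71 to 0.84 for Mann-Whitney and 0.33 to 0.47 for Fisher, so the advantage does not depend on exact normality.

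**Would the benchmark catch it?** With HEP truly at 75%, its own observed percentage falls below 80% in about 72% to 80% of trials. If credibility is judged pooled, 89% with 75% still passes the 80% benchmark about 73% to 76% of the time.

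**What the score comparison can deliver.** The 95% interval half-width is about 1.96√(2/n): 0.36 SD at 60 per arm, 0.40 at 48 and 0.41 at 45, before clustering. Section 6 gives groups of about 4 to 10. With an assumed intraclass correlation of 0.01 to 0.05, the design effect 1 + (m − 1)ICC runs from 1 + 3 × 0.01 = 1.03 to 1 + 9 × 0.05 = 1.45. Intervals would then be up to √1.45 = 1.20 times as wide. The powers in the table ignore clustering, which would lower both columns. No power was computed for sessions attended, and the CSQ-3 was not modelled separately.

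**The case against.** The pre-set criteria are the benchmarks, and no decision is tied to a Fisher p-value. Section 2 does not list showing that HEP is comparably credible as an aim, and the plan openly admits low power. Counts by arm must exist for the Fisher tests, so a HEP rate well below 80% would often be visible directly: at a true 70% its observed rate falls below 80% in 91% to 94% of trials. All of this stands, and it makes the point an improvement to a secondary comparison.

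A reader might infer that Fisher's test would usually miss any gap large enough to undermine HEP as a control. The documents do not support that. No credibility gap is named as important, and power exceeds one half at 89% against 70%. A 0.5 SD difference with 80% to 89% of the weaker arm above midpoint does give Fisher power of only 0.10 to 0.31, but both arms then sit at about or above the 80% benchmark. Nor do the documents say that a non-significant test would be taken as comparability, or that scores are lost; they stay in the dataset and only the planned comparison leaves them unused.

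On enrolment, the sentence can fairly be read as applying where a comparison is possible. That makes it a wording correction only.

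What the objection does not answer is that for moderate gaps the planned comparison uses the weaker summary of data already collected. By-arm reporting of credibility is also not stated; only attendance is specified for each program.

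**Conclusion.** The point holds as a cheap improvement. For a 14-point gap (89% against 75%), the planned test detects the difference 31% to 43% of the time, against 74% to 85% for mean scores from the same participants. The shortfall is greatest for moderate gaps, up to about 16 to 19 points, and shrinks beyond that. No estimate is biased and no benchmark changes.

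The figures rest on two-sided alpha 0.05, 1:1 allocation, normal underlying scores, assumed HEP rates and no clustering; the documents fix none of these. Even the score comparison leaves uncertainty of at least about 0.36 SD either way, so it would describe the difference without proving the two programs equally credible.

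**What to change.** - Keep the midpoint and 7-of-10-session percentages as benchmarks, and state that each is reported by arm.
- Add the between-arm mean difference with a 95% confidence interval for the CEQ credibility score, the CSQ-3 score and the number of sessions attended. Adjust for site and allow for clustering by therapy group, since a model with site alone could give intervals that are too narrow. Use a bootstrap or permutation interval, respecting the groups, if scores are skewed.
- Interpret the interval, and state that a non-significant Fisher test is not evidence of comparable credibility.
- Limit the enrolment comparison to sites.

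The cost is a few sentences in Section 9 and a little more analysis, with no new data. Intervals will be somewhat wider once group clustering is allowed for. Specifying this before scores are seen avoids a post hoc choice.

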## 10. Monitoring and Quality Assurance

The MPIs will monitor the validity of the data and adherence to the IRB approved protocol on a daily basis. A member of study staff will verify that all items on all questionnaires have been addressed. Data will be checked for out of range values using frequency distributions prior to analyzing the data. The MPIs will be responsible for ensuring compliance with IRB procedures.

- *Ongoing monitoring*: For each intervention session, an intervention checklist will be completed, detailing the information and exercises covered per session. Study therapists will undergo weekly supervision. All intervention sessions will be audio-recorded.

Participant Confidentiality. All study materials will identify participants only by study ID, visit number, and visit date. The study research assistant will be trained in procedures to protect study participant confidentiality. Recordings of each session will be immediately de-identified (e.g., only ID, visit number and date) and stored on a password protected computer; the recording will be subsequently and immediately deleted from the recording device.

Data Validity and Security. The research team will develop standard operating procedures for data collection, data management, and quality control. Drs. [name] and [name] will oversee all procedures related to secure data collection and management, along with [name] and the project manager. Electronic information will be stored in REDCap (Research Electronic Data Capture), a free, secure, and HIPAA-compliant web-based application hosted by the Partners HealthCare Research Computing Enterprise Research Infrastructure & Services (ERIS) group (based at the PHS Needham

corporate datacenter). All data will be stored on password protected computers that will be stored in secure locations at all times. Only research staff will have access to these data locations.

Participants' data will be identified by an ID number only, and a link between names and ID numbers will be kept on a separate folder on a Partners DropBox. Recordings will be immediately deleted from the digital recording device and stored under password protection. Among the 3 recruitment sites (MGH, Duke, Rush), PHI will be shared related to enrolled study participants. MGH will send and receive PHI to/from Duke and Rush using encrypted email as well as shared storage in the Partners-approved platform Dropbox. This PHI will be shared as sparingly as possible, but may include sharing names, ages, and contact information, among other identifiers. PHI will not be shared with any study collaborators outside of MGH, Duke, and Rush.

Data from this study will be stored for seven years after the publication of all study results, at which time all paper screening and consent forms will be shredded, and computer files will be deleted.

## **10.1 Review and Report Adverse Events and Unanticipated Problems**

If the research team identifies an adverse event (e.g., via study participants, research team members, clinicians, or review of electronic health records), we will follow the steps below:

**Serious Adverse Events.** Any event that meets the FDA definition of a serious adverse event or that is deemed by the research team or safety and monitoring committee to impose significant hazard, contraindication, side effect, or precaution, will involve expedited review. All relevant information will be reported to the committee via secure e-mail within 2 days. The committee will review the information and determine the extent to which the event was relevant to the study procedures. Reporting to the IRB will be done within 24 hours; reporting to NIA (including responses of the committee and the IRB) will be done within 7 days.

**Non-Serious Adverse Events.** Per study year and at study completion, the data safety and monitoring committee will receive a summary of adverse events per randomized group, including number and types of events, severity, time point, and determination of whether the events were study related.

**Study Stopping Rules.** Given low risk associated with this behavioral study, we have not identified a stopping rule. However, during the study period, if the data safety and monitoring committee deems that participant risk outweighs participant benefit, the committee may choose to recommend study termination.

## **10.2 External Factors That May Impact Participant Safety or Study Ethics**

[name] and [name] will review relevant literature at least twice per study year to ensure that no new developments may affect the study or participants. The study will not place limits on usual care and all activities will be conducted over and above what patients and caregivers normally receive as part of usual care.
